9.7 Secondary study parameter(s)

Secondary outcomes will include cardiopulmonary exercise testing (CPET), Health-related quality of life (HRQL), Sit-to-Stand test, hand grip strength, body composition, stair climb test, Physical activity level measured through an activity questionnaire, derived from the Community Health Activities Model Program for Seniors (CHAMPS), depression and anxiety assessed by GAD-7 and PHQ-9, nutritional status, compliance, length of hospital stay, and costs.

All secondary outcomes will be described as means plus SD or median plus IQR where data are continuous and normally respectively non-normally distributed measures, per time point. Categorical parameters will be described as number plus percentage per time point. Statistical methods will include t-test and Mann-Whitney U test for continuous normally respectively non-normally distributed parameters at a single time-point post-operatively. Categorical outcomes will be analyzed by using Chi-square tests or (logistic, ordinal or nominal, depending on the definition of the parameter) regression analysis for single time points.

To accommodate the repeated nature of the data and describe time effects, we will apply a generalized linear mixed model using the appropriate link-function (i.e. linear, poisson, logistic etc.).

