- Diet and rest: the diet is focused on a protein intake of 1,5-1,8 g/kg/day with 0,4 g/kg/day whey proteins after training and 0,4 g/kg/day casein proteins before bedtime. This is further explained in the nutrition section of the protocol.

With the training program we try to achieve the following improvements:

- Increase of 10% of VO₂-peak
- Increase of 15% of VO₂-peak at AT
- Increase of 20-40% in 1RM tests (or increase in dumbbell weight)
- Increase in the distance of 10% at 6MWT (at <500m)
- Decrease of 10% of the stairs climb test

At baseline, after prehabilitation (1 week before surgery) and 4 weeks after surgery CPET will be performed. At baseline, the week before surgery, 4 and 8 weeks postoperatively, muscle strength will be tested with the sit-to-stand test, 1-RM and handgrip strength. Functional capacity will be tested at the same time points using the 6-minute walk test and stair climb test. Patients in both groups will wear an accelerometer during four weeks before surgery and four weeks after surgery in order to estimate (changes) in physical activity outside of the hospital in the control and intervention group.

Determine AT:

While slowly increasing the resistance, the VO₂, VCO₂ and VE (expired ventilation) will initially rise linear, up to the moment lactic acidosis develops. With effort above the anaerobic threshold (AT) the CO₂ rises faster than the O₂ uptake, because the CO₂ produced from HCO₃⁻, by buffering lactate, is added to the CO₂ production. VE rises with the increase of CO₂ output (isocapnic buffering), there is still a linear relation whereby EQCO₂ (VE/VCO₂) remains constant (or a light decrease), while EQO₂ (VE/VO₂) increases.

- Increase of VE/VO₂, while VE/VCO₂ remains constant (or light decreases).
- Increase of PETO₂ (change in linearity) vs workload.
- V-slope: change in linearity of VO₂ vs VCO₂

Determine RCP:

If the workload (Watt) after AT further increases, VE rises faster than de CO₂ output, i.e. a rise of EQCO₂ (VE/VCO₂), which ensures for a decrease of PaCO₂ and PETCO₂ (hyperventilation). The point at which the VE rises more than needed for the CO₂, and the PETCO₂ decreases is a 'extra' ventilatory response and is also called 'respiratory compensation point' (RCP). The increase of H⁺ concentration stimulates the carotic bodies (vascular glands) to increase the ventilatory drive as a reaction at the lactic acidosis. By an increase of VE the arterial PCO₂ decreases.

- Increase of VE/VCO₂ vs workload

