8.2 Randomization, blinding and treatment allocation

Patients will be randomized by block randomization with a block size of 8, with a 1:1 allocation by means of randomization software, stratified by study sites, neoadjuvant therapy vs. no neoadjuvant therapy and tumour location (colon/rectum). Patients will be allocated either to the prehabilitation intervention group, receiving 4 weeks prehabilitation, or to the control group, receiving no prehabilitation (standard care). Both groups will receive 8-week rehabilitation following the current international ERAS guidelines. Similarly all the perioperative care will follow the ERAS guidelines for colorectal surgery.

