- Health-related quality of life (HRQL) as measured by the acute (1 week recall period) RAND health survey (19) and the EORTC QLQ-C30 for cancer patients and EORTC QLQ-CR29 specifically for colorectal cancer patients. The RAND is the most widely used HRQL measure and has been validated for surgical population (20). It incorporates behavioral functioning, subjective well-being and perceptions of health by assessing, on a 0 to 100 scale, eight health concepts: (1) Physical function (PF) -limitations in physical activities due to health problems; (2) Role physical (RP)-limitations in role activities due to physical health problems; (3) Role emotional (RE) -limitations in usual role activities due

to emotional problems; (4) Social functioning (SF) –limitations in social activities due to health problems; (5) Bodily pain (BP)-pain; (6) General health (GH) -general health perceptions; (7) Vitality (VT) -energy and fatigue; and (8) Mental health (MH) -general mental health. Two summary scores have been developed: the Physical Component Summary (PCS) and the Mental Component Summary (MCS)), standardized to have a mean of 50 and a standard deviation of 10. A higher score on the RAND sub-scales or component summary measures indicates a better quality of life. A change of as little as two units on the PCS has been shown to be the minimum clinically meaningful change; 5 points is often targeted by medical intervention studies, though surgical interventions can have an impact as large as 10 points. The RAND and EORTC QLQ-CR29 and EORTC QLQ-C30 will be measured at baseline, before surgery, 4 weeks, 8 weeks and 1 year after surgery.

- The vulnerability of older patients will be measured by two different scores, the Fried frailty score and the G8 score. The Fried Frailty Score will be looked at (baseline) to determine whether the patient can be classified as frail based on five different categories such as weight loss, weakness through hand grip, endurance, slowness and activity level.¹¹⁵ The G8 score is an instrument based on 8 different items to identify a geriatric risk profile in patients and has a strong prognostic value for deterioration and survival.¹¹⁶ It has a high sensitivity and negative predictive value to assess the fragility of older patients with cancer who will go for elective abdominal surgery and will be measured at the start of the study.¹¹⁷

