- Physical activity level will be measured through an activity questionnaire derived from the Community Health Activities Model Program for Seniors (CHAMPS) questionnaire.¹¹⁸ This questionnaire is a self-reported measure of physical activity, comprising 18 activities evaluated according to the total number of hours done during an average week. Physical activity will be measured at baseline, before surgery, and at 4 and 8 weeks after surgery. More objective levels of physical activity are assessed using an accelerometer, a small and lightweight device, which detects accelerations. Patients in both the intervention and control group will wear the accelerometer for 4 weeks. Although accelerometers may underestimate some activities, such as cycling and water activities, it is recognized as a reasonably valid tool to objectively assess physical activity.^{119,120,121,122} Accelerations are converted into activity counts per minute, indicating the level of physical activity.
- Depression and anxiety will be assessed by the GAD-7 and PHQ-9 questionnaires at baseline, before surgery, and at 4 and 8 weeks after surgery. The GAD-7 is a valid and efficient tool for screening for generalized anxiety disorder (GAD) and assessing its severity in clinical practice and research.¹²³ The PHQ-9 including nine questions, is half the length of many other depression measures, has comparable sensitivity and specificity, and consists of the actual nine criteria on which the diagnosis of DSM-TV depressive disorders is based.¹²⁴
- Compliance with the interventions is assessed by self-report, and attendance and exercise logs filled in by either the physical therapists or kinesiologist and psychologist (e.g. observed attendance at and compliance with the exercise). Non-responders and dropouts receive a short questionnaire to assess the reason for non-participation or dropping out of the study. Satisfaction with intervention after completion of the intervention programs, patients are asked to complete a brief questionnaire addressing the perceived efficacy of and satisfaction with the program, whether they would suggest any changes to the program and if they would recommend it to other patients undergoing similar treatments.

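### Section 9.7 names unadjusted single-visit tests and a mixed model for continuous secondary outcomes without saying which gives the between-arm result, and the tests use neither baseline nor randomisation strata

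*Protocol*

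**What the plan says.** Section 9.7 of the Protocol sets two analyses for the continuous secondary outcomes. The first is a two-sample test: "Statistical methods will include t-test and Mann-Whitney U test for continuous normally respectively non-normally distributed parameters at a single time-point post-operatively". The second follows in the next paragraph: "To accommodate the repeated nature of the data and describe time effects, we will apply a generalized linear mixed model", with a link function suited to the outcome. Section 9.7 does not say which is inferential where both could apply, or whether baseline is a covariate or one of the responses.

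Baseline values are collected for most of these outcomes:

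- Quality of life (Section 8.3): "The RAND and EORTC QLQ-CR29 and EORTC QLQ-C30 will be measured at baseline, before surgery, 4 weeks, 8 weeks and 1 year after surgery".
- Anxiety and depression (Section 8.3): "Depression and anxiety will be assessed by the GAD-7 and PHQ-9 questionnaires at baseline, before surgery, and at 4 and 8 weeks after surgery".
- Strength (Section 5.1): "At baseline, the week before surgery, 4 and 8 weeks postoperatively, muscle strength will be tested with the sit-to-stand test, 1-RM and handgrip strength".
- Cardiopulmonary exercise testing, stair climb, the activity questionnaire, PG-SGA and weight (Sections 5.1 and 8.3, Appendix I): also at baseline.

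Length of stay, compliance and costs, which 9.7 lists as well, have no usable pre-randomisation value. Section 8.2 stratifies randomisation by site, neoadjuvant therapy and tumour location. Section 9.7 does not mention these factors.

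**The concern.** Fitness, strength and questionnaire scores differ between patients before any treatment. A two-sample test on the post-operative value leaves those differences in the error term. It also leaves any chance baseline imbalance between the arms uncorrected. If the strata are prognostic, ignoring them makes the standard error larger than the stratified design warrants.

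The second issue is choice. An outcome measured at several visits can be given both a single-visit test and a mixed-model contrast, and the two can disagree. With no statement of which one counts, the choice could be made after the results are seen. At stake are the precision and clarity of the secondary results. The primary endpoints are handled separately in Section 9.6.

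**Working it through.** **1. The plan's own figure.** The only sample size the Protocol derives is for the Comprehensive Complication Index (Section 4.4): mean 10.4, SD 14, 30% reduction, two-sided alpha 0.05, power 0.80, 10% dropout.

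- Difference: 0.30 × 10.4 = 3.12.
- Per arm: 2 × (1.96 + 0.842)² × 14² / 3.12² gives 317 after rounding up.
- With dropout: 317 / 0.90 gives 353 per arm, 706 in total. The Protocol states 354 and 708, so its figure is reproduced.
- Evaluable per arm: 354 × 0.90 ≈ 319, used below.

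No SD, power or correlation is given for any secondary outcome.

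**2. Standard error with and without baseline.** Let r be the within-arm correlation between baseline and the post-operative value. For a difference in means with n per arm and SD σ:

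- two-sample test: SE = σ√(2/n)
- ANCOVA: SE = σ√(2(1 − r²)/n)
- ratio = 1/√(1 − r²); sample size for equal precision scales as 1/(1 − r²)

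The difference detectable with 80% power and 319 per arm is 2.80 × √(2/319) × √(1 − r²), in SD units. The last column is the adjusted power for an effect that the unadjusted test detects with 80% power: Φ(2.80/√(1 − r²) − 1.96).

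| r (assumed) | SE ratio, unadjusted/adjusted | Extra patients for equal precision | Detectable difference, adjusted | Power, adjusted |
|---|---|---|---|---|
| 0 | 1.000 | 0% | 0.222 SD | 80% |
| 0.3 | 1.048 | 10% | 0.212 SD | 84% |
| 0.5 | 1.155 | 33% | 0.192 SD | 90% |
| 0.7 | 1.400 | 96% | 0.158 SD | 97% |
| 0.8 | 1.667 | 178% | 0.133 SD | >99% |

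The Protocol gives no r. Section 8.3 cites a test-retest reliability of 0.73 to 0.99 for the six-minute walk test. That is the repeatability of a primary outcome in other populations, not a correlation across surgery for a secondary one, so it does not fix r.

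**3. Does the planned mixed model recover the loss?** This was checked by generalized least squares with four visits (baseline, pre-operative, 4 and 8 weeks), equal correlation r between visits, complete data, SD 1 and 319 per arm. The contrasts are at the last visit.

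| r | SE, free arm-by-visit means | SE, change-from-baseline contrast | SE, arm baseline means set equal |
|---|---|---|---|
| 0.3 | 0.0792 | 0.0937 | 0.0755 |
| 0.5 | 0.0792 | 0.0792 | 0.0686 |
| 0.7 | 0.0792 | 0.0613 | 0.0565 |

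With free arm-by-visit means, the single-visit SE is √(2/319) = 0.0792 whatever r is, the same as the two-sample test. The change-from-baseline contrast lies above the constrained model by 24%, 15% and 8%. Setting the arms' baseline means equal gives the ANCOVA SE. Whether the planned model helps therefore depends on a specification that 9.7 does not give.

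**4. Strata.** The Protocol gives nothing from which to size the loss from ignoring them, so no figure is put on it. Adjusting is cheap: with six sites (Section 3), main effects use 5 + 1 + 1 = 7 degrees of freedom out of about 638 evaluable patients.

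**The case against.** The strongest reply is that 9.7 already contains the remedy. The outcomes with a baseline are measured repeatedly, and the mixed model is there for repeated data. On this reading the two-sample tests are meant only for outcomes with one post-operative value, such as those at the end of the list: "nutritional status, compliance, length of hospital stay, and costs". The order of the section fits this reading, but it does not remove the point. The sentence is not limited to such outcomes. In Sections 5.1 and 8.3 and the English schedule in Appendix I, cardiopulmonary exercise testing has a baseline and just one post-operative visit, at week 4 (only the Italian flow chart adds week 8). VO₂max would therefore still get the unadjusted test.

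A reader might go further and infer that the plan as a whole discards baseline. The documents do not support that, because the mixed model can use it. Nor do they settle that the model is merely descriptive. Section 9.6 gives its mixed model the task of testing the arms, whereas 9.7 speaks only of repeated data and time effects. That is an ambiguity rather than a decision.

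It can also be said that covariates and contrasts belong in the statistical analysis plan, which the Protocol promises and which is not shown, and that the list of methods is not exhaustive. This stands for the missing model details. It does not cover the unadjusted test, which the Protocol itself names.

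Finally, the effect is modest. The trial is sized for a primary endpoint, no power target exists for secondary outcomes, and 319 per arm already detect 0.222 SD unadjusted. That stands and limits the weight of the point.

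**Conclusion.** The point holds as one of precision and clarity. For continuous secondary outcomes with a baseline value, the tests named in 9.7 ignore that value and the strata, and the section does not say whether they or the mixed model give the between-arm result. The standard error of a comparison of means is larger than needed by 1/√(1 − r²), about 5% to 67% for r from 0.3 to 0.8.

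A narrower range, such as 15% to 40%, would be tempting to quote as fact. It requires r of about 0.5 to 0.7, which the documents do not supply. The formula is for means and does not carry over directly to the Mann-Whitney test. It does not apply to length of stay, compliance or costs.

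Nor should a reader infer bias or an invalid test. Under randomisation the unadjusted comparisons are valid, and ignoring prognostic strata makes them conservative. What is lost is precision in secondary outcomes.

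**What to change.** In Section 9.7, for continuous outcomes with a baseline value, take the between-arm contrast at each post-operative visit from one model and name it as the inferential analysis. This can be ANCOVA, or the planned mixed model with baseline as a covariate or with the arms' baseline means constrained equal. Include site, neoadjuvant therapy and tumour location as fixed effects. Keep the t-test and Mann-Whitney test only for outcomes without a baseline: length of stay, compliance and costs.

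The cost is a short change to 9.7, submitted as an amendment under Section 11.3, and matching text in the statistical analysis plan before any comparison of the arms is seen. No new patients, visits or measurements are needed.

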2. OBJECTIVES

Primary Objective: To investigate if multimodal prehabilitation could decrease postoperative complications and improve functional capacity pre- and postoperatively for patients undergoing colorectal surgery for cancer.

Secondary Objective(s): To investigate the effects of multimodal prehabilitation on Health Related Quality of Life, nutritional status, length of hospital stay and cost-effectiveness.

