8.1.2 Secondary study parameters/endpoints (if applicable)

Secondary outcomes include Patient Reported Outcome Measurements (PROMs) such as health related quality of life (HRQoL) (EORTC QLQ-CR29 and EORTC QLQ-C30, RAND questionnaires) and depression and anxiety scores (GAD-7, PHQ-9 questionnaires), functional capacity (VO₂max, sit to stand test, stair climb test, 1-RM, hand grip strength and self-reported physical activity), nutritional status, length of hospital stay, study compliance, and a cost-effectiveness analysis.

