- Costs of the exercise programs, data on health care costs, patient and family costs and costs of production losses are collected using monthly cost diaries measured on a three-monthly basis during the entire follow up period. Health care costs include the costs of oncological care, general practice care and physiotherapy, additional visits to other health care providers, prescription of medication, professional home care and hospitalization. Patient and family costs include out-of-pocket expenses such as travel expenses and costs for paid and unpaid help. Costs related to production losses include work absenteeism for patients (or parents) with paid jobs and days of inactivity for patients (or parents) without a paid job.

Patients will return to the hospital at 4 and 8 weeks to see either the sport physician or physiotherapist/kinesiologist, as well to collect the postoperative data. Questionnaires for PROMs will be additionally performed 1 year post surgery. We will also measure surgical reinterventions, chemotherapy, hospital visits and mortality 1 year postoperatively.

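### Protocol section 9.7 gives costs the default summary for skewed secondary outcomes (median, IQR, Mann-Whitney), which does not estimate the mean cost difference that the cost-effectiveness objective needs

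*Protocol*

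**What the plan says.** Section 9.7 ends its list of secondary outcomes with "nutritional status, compliance, length of hospital stay, and costs". It then gives a descriptive rule for the whole list: "All secondary outcomes will be described as means plus SD or median plus IQR where data are continuous and normally respectively non-normally distributed measures". The testing rule follows the same switch: "Statistical methods will include t-test and Mann-Whitney U test for continuous normally respectively non-normally distributed parameters at a single time-point post-operatively". For repeated data it adds that "we will apply a generalized linear mixed model using the appropriate link-function (i.e. linear, poisson, logistic etc".). Costs are not exempted from any of this.

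Cost-effectiveness appears separately. Section 2 makes it a secondary objective ("nutritional status, length of hospital stay and cost-effectiveness"), and section 8.1.2 lists it as an outcome ("length of hospital stay, study compliance, and a cost-effectiveness analysis"). Section 8.3 says that costs, including hospitalization, are collected "using monthly cost diaries measured on a three-monthly basis during the entire follow up period". It does not say how they are compared between arms or combined with effects. The opening of the statistical section defers detail to a statistical analysis plan, which is not at hand.

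**The concern.** A cost-effectiveness analysis sets the difference in arithmetic mean cost against the difference in mean effect. Mean cost times the number of patients is what the payer spends. A median difference is a different quantity, and a rank test estimates neither.

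Skewed costs are likely here. Section 1 links complications to higher hospital costs, and section 9.6 expects the complication index itself to be right-skewed. The normality switch therefore probably sends total cost per patient to median, IQR and Mann-Whitney.

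This trial is also one where mean and median can part. The programme in section 5.1 (supervised sessions three times a week, supplements, dietary advice, weekly calls) adds cost to every prehabilitation patient. Any saving comes from fewer patients in the expensive tail. Ranks register the small shift common to all and give little weight to the size of the tail. At stake is whether the cost result reported under section 9.7 agrees with the cost-effectiveness result it is meant to support.

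**Working it through.** **The plan's own figure.** The only sample size is for the complication index (section 4.4): mean 10.4, SD 14, 30% decrease, alpha 0.05 two-sided, power 0.80, 10% dropout. The difference is 0.30 × 10.4 = 3.12. n per arm = 2 × (1.960 + 0.842)² × 14² / 3.12² ≈ 317. Inflated for dropout, 317 / 0.90 ≈ 353 per arm, or 706 in total against 708 stated. It reproduces, and the point does not turn on it. Evaluable patients are about 354 × 0.90 ≈ 318 per arm. No figure is stated for costs.

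**Exact example without sampling.** Costs are in assumed thousands, 318 per arm. Control: 223 patients at 10 and 95 at 30. Prehabilitation: 251 at 11 and 67 at 31.

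- Control mean = (2,230 + 2,850) / 318 = 15.97. Prehabilitation mean = (2,761 + 2,077) / 318 = 15.21. Prehabilitation is cheaper by 0.76.
- Medians are 10 and 11. Prehabilitation is dearer by 1.
- Mann-Whitney: the chance that a prehabilitation patient costs more than a control patient = (251 × 223 + 67 × 318) / 318² = 77,279 / 101,124 = 0.76, p < 0.001 in the dearer direction.

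Mean and rank result can therefore have opposite signs.

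**How often, under assumed costs.** All costs here are assumptions. Cost = lognormal base (mean 10,000, CV 0.25) + lognormal extra cost in complicated patients (CV 1.2) + programme cost in the prehabilitation arm. Complication risk is taken as 30% lower with prehabilitation; that figure is borrowed from the index target in section 4.4. True mean difference = programme cost − 0.30 × control risk × extra cost; for A, 1,000 − 0.09 × 15,000 = −350.

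| | Control risk | Programme | Extra | True mean difference | Significantly dearer by Mann-Whitney, 354 per arm (repeated runs) | 318 per arm |
|---|---|---|---|---|---|---|
| A | 30% | 1,000 | 15,000 | −350 | 37–42% | 37% |
| B | 30% | 1,500 | 20,000 | −300 | 85–89% | 79% |
| C | 40% | 1,500 | 15,000 | −300 | 48–55% | 48% |
| D | 50% | 1,500 | 15,000 | −750 | 12–14% | 11% |

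The median difference is about +510 to +530 in A and about +950 in B, against a negative mean difference in both.

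**How typical A to C are.** The full grid has risk 30/40/50%, programme 500/1,000/1,500 and extra 10,000/15,000/20,000, so 27 cells. In five the programme cost equals or exceeds the saving (mean difference +100, +600, +150, +300 and 0). That leaves 22 where prehabilitation is truly cheaper. A to C lie at or near the top of these. In about 16 of the 22 the figure is around 10% or less, and in several it is about 0%.

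**Sensitivity to base-cost variation.**

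- At base-cost CV 0.4 to 0.6 with 318 per arm, A to C fall to roughly 6% to 40%.
- At CV 0.15, A rises to about 90%.
- Rarer, dearer complications push the figure up. With 20% versus 14% at 30,000 each and programme cost 1,000, the mean difference is 1,000 − 0.06 × 30,000 = −800. Mann-Whitney says dearer in 29% of trials at CV 0.40, 65% at 0.25 and 99% at 0.15 (extra-cost CV 1, 318 per arm).
- At 50% versus 35% risk, extra cost 12,000 to 20,000 and programme cost 500 to 1,000, mean and median agree in sign and the figure is 1% or less.

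**The alternative on the same data.** A Welch comparison of means was significant against prehabilitation in under 2% of trials in A to D.

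**The case against.** The strongest reply is textual. The test sentence covers parameters at a single post-operative time point and says only what the methods will include. Costs come from diaries spread over follow-up, and the next paragraph of section 9.7 offers repeated data a mixed model with a suitable link, which models means. The cost-effectiveness analysis is a separate item in section 8.1.2 with no stated method, and nothing says its ratio is built from medians. All of this stands. A reader might infer that the plan makes a cost-effectiveness analysis impossible; the text does not support that.

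What does not fall away is the descriptive rule. It covers all secondary outcomes and has no exclusivity gap for costs. Total cost per patient is also one value per patient, so the single-time-point test is its natural home even though the text does not order it.

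A reader might also infer that the cost result will come out with the wrong sign. The documents cannot support that either: they contain no costs, and the only complication rate given is up to 50% (section 1), at which the reversal largely vanishes in the grid. The mean difference is itself imprecise. In A to C the true saving of 300 to 350 compares with a standard error of about 900 to 1,150, so the observed mean difference has the wrong sign in about 36% to 38% of trials, though rarely significantly.

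Finally, the type of bootstrap, paired resampling and acceptability curves belong in the statistical analysis plan or a health-economics plan. Their absence from the protocol is no fault.

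**Conclusion.** The point holds as a badly chosen default and is minor. Section 9.7 names costs, applies the normality switch to them without exception, and so steers skewed total costs to summaries that do not estimate the mean cost difference required by the objective in section 2. That mismatch needs no assumed costs; it needs only that costs are judged non-normal, which is likely but which the protocol does not state.

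The practical size does rest on assumptions. In the grid at base-cost CV 0.25, with prehabilitation truly cheaper on the mean, a significant rank result against it occurred in about 0% to 89% of simulated trials, mostly about 10% or less. Tighter base costs or rarer, dearer complications raise the figure, and more variable base costs lower it. A conflict in sign is possible, not expected.

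**What to change.** Add one sentence to section 9.7 and mirror it in the statistical analysis plan: *Costs are exempt from the normality rule; total cost per patient over follow-up is compared as the difference in arithmetic means between arms, with a confidence interval suited to skewed data, and this difference is used in the cost-effectiveness analysis; median and IQR are descriptive only.* A bootstrap interval would serve, as would a generalized linear model (for example gamma with log link) if its result is reported as a mean difference. The choice can be left to the analysis plan.

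The change needs no extra data or patients. Its price is an interval that will be wide and less likely to reach significance than a rank test.
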